4.2.3.3 Management of mucositis/stomatitis

General and grade specific recommendations are described in Table 4.2.3.3:1. For dose adjustment refer to Section 4.1.4.1.2 and for restrictions on concomitant therapies refer to Sections 4.2.2 and 10.1.

Treatment is supportive and aimed at symptom control. These may include atraumatic cleansing and rinsing with non-alcoholic solutions such as normal saline, diluted salt and baking soda solution (e.g. one-half teaspoonful of salt and one teaspoon of baking soda in one quart of water every four hours); avoidance of agents containing iodine, thyme derivatives and prolonged use of hydrogen peroxide; dietary manoeuvres such as promotion of soft, non-irritating foods like ice-creams, mashed/cooked vegetables, potatoes and avoidance of spicy, acidic or irritating foods such as peppers, curries, chillies, nuts and alcohol. If the patient is unable to swallow foods or liquids, parenteral fluid and/or nutritional support may be needed. Examples of some of the agents suggested in Table 4.2.3.3:1 include: topical analgesics –viscous lidocaine 2%; mucosal coating agents - topical kaolin/pectin; oral antacids, maltodextrin, sucralfate; topical antifungals – nystatin suspension. (Adapted from 8)

Table 4.2.3.3: 1 Grade specific treatment recommendations of study-drug related mucositis/stomatitis

Severity (CTCAE grading)	Description	Treatment recommendations	Intervention concerning afatinib treatment/ dose modification
Mild (Grade 1)	Minimal symptoms; normal diet	Oral rinses with agents such as non-alcoholic mouth wash, normal saline, diluted salt and baking soda solution.	No change.

Moderate (Grade 2)	Symptomatic, but can eat and swallow modified diet	Addition of topical analgesic mouth treatments, topical corticosteroids, antiviral therapy if herpetic infection confirmed, antifungal therapy preferably topical on a case by case basis.	Maintain dose if tolerable; Hold dose if intolerable until recovery to grade ≤1, then restart at the same dose.
Severe (Grade 3)	Symptomatic and unable to adequately aliment or hydrate orally	Same as for Grade 2; institute additional symptomatic therapy (topical or systemic) as clinically indicated.	Hold dose until recovery to grade ≤2 or baseline, then restart at the reduced dose according to Section 4.1.4.
Life threatening (Grade 4)	Symptoms associated with life-threatening consequences	Same as for Grade 2; institute additional symptomatic therapy (topical or systemic) as clinically indicated.	Hold dose until recovery to grade ≤2 or baseline, then restart at the reduced dose according to Section 4.1.4

4.2.3.4 Management of interstitial lung disease (ILD) and keratitis

Careful assessment of all patients with an acute onset and/or unexplained worsening of pulmonary symptoms (dyspnea, cough, fever) should be performed to exclude interstitial lung disease (ILD). Study drugs should be interrupted pending investigation of these symptoms. If interstitial lung disease is diagnosed, study drug must be permanently discontinued and appropriate treatment instituted as necessary.

Patients who present with symptoms of keratitis, such as acute or worsening eye inflammation, lacrimation, light sensitivity, blurred vision, eye pain and/or red eye should be referred promptly to an ophthalmic specialist. If a diagnosis of ulcerative keratitis is confirmed, treatment with afatinib should be interrupted or discontinued. If keratitis is diagnosed, the benefits and risks of continuing treatment with afatinib should be carefully considered. Afatinib should be used with caution in patients with a history of keratitis, ulcerative keratitis or severe dry eye. Contact lens use is a risk factor for keratitis and ulceration.

4.3 TREATMENT COMPLIANCE

Patients will be dispensed Afatinib on a monthly basis in pill bottles with 30 tablets each. At every follow-up visit, they will be asked to bring in their pill bottles and pill count will be

performed. Pill diary will also be provided to document every dose taken. Missed doses and compliance to treatment will be documented.

5. VARIABLES AND THEIR ASSESSMENT

5.1 TRIAL ENDPOINTS

5.1.1 Primary endpoint(s)

Objective Response Rate (Complete Response + Partial Response), defined by tumor shrinkage (mm), per Response Evaluation Criteria in Solid Tumors (RECIST) v1.1.

5.1.2 Secondary endpoint(s)

Duration of response (measured in weeks), Progression-free survival (PFS) in weeks, overall survival (OS) in months, toxicity assessments using CTCAE v4.0, analysis of tumor-tissue microarrays by high-quality immunohistochemical assays and automated image analysis (AQUA, Genoptix®) from biopsies obtained at baseline, after four weeks of treatment with the combination, and again at disease progression or end of treatment.

5.2 ASSESSMENT OF EFFICACY

Response and progression will be evaluated in this study using Response Evaluation Criteria in Solid Tumors (RECIST) guideline (version 1.1) (9). Tumor response will be assessed by investigator.

See APPENDIX 10.4, RECIST 1.1 Criteria for details on lesion measurements and response assessment.

5.3 ASSESSMENT OF SAFETY

The safety of afatinib will be assessed through collection and analyses of adverse events (AEs) and laboratory tests. AE's and their management will be recorded at every treatment and follow-up visit while subjects are on study. SAE's will be appropriately reported as per Section 5.3.7.

5.3.1 Physical examination and ECOG performance status

A physical examination will be performed as part of the screening visit prior to initiation of study treatment. Subsequently, patients will be seen for every cetuximab dose. A physical examination and ECOG performance status will be recorded at every evaluation.

5.3.2 Vital signs

Vital signs will be recorded at every visit as outlined in Section 5.3.1 above.

5.3.3 Safety laboratory parameters

Baseline Complete Blood Count (CBC) with differential, Comprehensive Metabolic Panel (CMP) and Magnesium levels will be obtained at the Screening visit to ensure eligibility criteria are

met. These laboratory evaluations will be repeated prior to every cetuximab dose throughout treatment. In addition, for women of childbearing potential, urine/serum Human Chorionic Gonadotropin (HCG) test will also be obtained at least every 4 weeks. Coagulation studies are recommended every 4 weeks for patients on anticoagulation therapy (excluding a daily baby aspirin).

5.3.4 *Electrocardiogram*

Baseline EKG will be obtained at the screening visit to rule out active cardiac issues. Subsequent EKG's will be obtained as clinically indicated.

5.3.5 *Other safety parameters*

Studies such as Echocardiogram and Pulmonary Function Tests, etc. will be obtained as clinically indicated for individual patients.

5.3.6 *Assessment of adverse events*

5.3.6.1 Definitions of adverse events

Adverse event

An adverse event (AE) is defined as any untoward medical occurrence in a patient or clinical investigation subject administered a medicinal product and which does not necessarily have to have a causal relationship with this treatment.

An AE can therefore be any unfavourable and unintended sign (including an abnormal laboratory finding), symptom, or disease temporally associated with the use of a medicinal product, whether or not considered related to the medicinal product.

Serious adverse event

A serious adverse event (SAE) is defined as any AE which:

- results in death,
- is life-threatening,
- requires inpatient hospitalisation or prolongation of existing hospitalisation,
- results in persistent or significant disability or incapacity,
- is a congenital anomaly/birth defect,

or

- is to be deemed serious for any other reason if it is an important medical event when based upon appropriate medical judgment which may jeopardize the patient and may require medical or surgical intervention to prevent one of the other outcomes listed in the above definitions.

Life-threatening in this context refers to an event in which the patient was at risk of death at the time of the event; it does not refer to an event that hypothetically might have caused death if more severe.

If cancer is the indication for treatment, only cancers of new histology and cases where there is clear evidence of exacerbation of an existing cancer qualify as a serious event.

Every new occurrence of cancer must be reported as a serious event regardless of the duration between discontinuation of the drug and the occurrence of the cancer.

Severity of adverse event

The severity of adverse events should be classified and recorded according to the Common Terminology Criteria for Adverse Events (CTCAE) v 4.03. in the (e)CRF.

For events not listed in the CTCAE, severity will be designated as mild, moderate, severe or life threatening, or fatal which respectively correspond to Grades 1, 2, 3, 4, and 5 on the NCI CTCAE, with the following definitions:

- **Mild:** An event not resulting in disability or incapacity and which resolves without intervention;
- **Moderate:** An event not resulting in disability or incapacity but which requires intervention;
- **Severe:** An event resulting in temporary disability or incapacity and which requires intervention;
- **Life-threatening:** An event in which the patient was at risk of death at the time of the event;
- **Fatal:** An event that results in the death of the patient.

Causal relationship of adverse event

Medical judgment should be used to determine the relationship, considering all relevant factors, including pattern of reaction, temporal relationship, de-challenge or re-challenge, confounding factors such as concomitant medication, concomitant diseases and relevant history. Assessment of causal relationship must be recorded for each adverse event.

Causality will be reported as either "Yes" or "No".

Yes: There is a reasonable causal relationship between the investigational product administered and the AE (i.e., the AE is possibly, probably, or definitely related to the investigational product).

No: There is no reasonable causal relationship between the investigational product administered and the AE.

5.3.7 Adverse event collection and reporting

5.3.7.1 AE collection

The following must be collected and documented on the appropriate CRF(s) by the Investigator:

- From signing the informed consent onwards through the Residual Effect Period (REP), until individual patient's end of trial (through the EOR or end of follow-up visit):
-all AEs (serious and non-serious) and all AESIs.
- After the individual patient's end of trial (after the EOR or end of follow-up visit, but including the overall survival follow-up period): the investigator does not need to actively monitor the patient for AEs but should only report relevant SAEs and relevant AESIs of which the investigator may become aware of.

For Afatinib the residual effect period (REP) is defined as 30 days after last intake of it.

5.3.7.2 Exemptions to SAE reporting

None

5.3.7.3 Information required

For each adverse event, the investigator should provide the onset date, end date, intensity, treatment required, outcome, seriousness, and action taken with the investigational drug. The investigator should determine the causal relationship and expectedness with the investigational drug to all AEs as defined in the listed adverse event section of Boehringer Ingelheim's (BI's) Investigator Brochure.

The following should also be recorded as an (S)AE in the (e)CRF and SAE form (if applicable):

- Worsening of the underlying disease or of other pre-existing conditions

- Changes in vital signs, EKG, physical examination and laboratory test results, if they are judged clinically relevant by the Investigator.

If such abnormalities already pre-exist prior trial inclusion they will be considered as baseline conditions

All (S)AEs, including those persisting after individual patient's end of trial must be followed up until they have resolved, have been sufficiently characterized, or no further information can be obtained.

5.3.7.4 Pregnancy

The sponsor-investigator shall be responsible to follow up on all information regarding a reported Drug Exposure during Pregnancy. The investigator shall ensure that any SAEs during and after pregnancy obtained by the Investigator will be reported to the Boehringer Ingelheim Unique Entry Point in the same format and timeline as any other SAE.

5.3.7.5 S(AE) reporting to Boehringer Ingelheim and NCCN

The sponsor-investigator must report all SAEs and non-serious AEs which are relevant for the reported SAE to BI by fax using BI IIS SAE form to BI Unique Entry Point as detailed below in accordance with the timelines specified in the safety exchange agreement

The SAE contact (fax number) is :

Boehringer Ingelheim Pharmaceuticals, Inc

[name]

[name]

[contact]

In addition, SAEs must also be sent to NCCN via email to [contact] or fax at [contact].

5.4 ASSESSMENT OF EXPLORATORY BIOMARKER(S)

Pre-treatment biopsies or archived tumor tissue (if no other systemic treatment was administered since that biopsy/excision) will be used to establish a baseline presence and quantification of EGFR, phosphorylated EGFR, and HER2 using immune-fluorescent staining and automated image analysis (AQUA, Genoptix®). These levels will then be compared with levels measured on tumor tissue obtained after 4 weeks of treatment with both Afatinib and Cetuximab to determine effects of treatment and again from tumor tissue obtained at the time of disease progression on treatment. Through sequential measurement of these biomarkers we hope to determine the prevalence of over expression in our patient population, whether EGFR,

phosphor-EGFR and HER2 levels change with treatment with dual EGFR inhibitors and correlate with clinical response and whether they can be used in the future as predictive of response to treatment.

Taking a core needle biopsy (CNB) is anticipated to be the most likely methodology employed in acquiring tissue for analysis in this patient group with advanced cancer of the head and neck region. This can usually be performed in a head and neck surgeon's office under local anesthesia. Tissue samples obtained from all participating sites will be transported to Yale Pathology to [name]'s lab for processing and analysis. Instructions for tissue acquisition and handling, and shipping of samples can be found in the study Laboratory Manual.

5.4.1 Biobanking

A tissue repository will be created from the tumor samples derived from patients enrolled on this study. All samples will be submitted to [name] MD (cell [contact]), Yale Head and Neck Biosample Repository ([name], Director) at [name]. Material may be archived for future use including but not limited to immunohistochemistry. Selected specimens will be processed for immediate patient-derived xenograft development in the [name] Lab. Collection of these samples will be coordinated with [name] [contact]), [name]. Development of patient-derived xenografts is conducted with funding from the Department of Defense [CA201045P1; PI: [name]].

5.4.2 Sequencing

Pre- and post-treatment tumor specimens from up to 50 enrolled patients will be submitted for whole exome sequencing to the Yale Center for Genome Analysis. Outcome will be analyzed by the presence or absence of *TP53* mutation, as well as *TP53* mutation class (disruptive, gain of function, non-disruptive). This work is conducted with funding from the Department of Defense [CA201045P1; PI: [name]].

6. INVESTIGATIONAL PLAN

6.1 VISIT SCHEDULE

The Trial Flow Chart summarizes the trial procedures to be performed at each visit. Individual trial procedures are described in detail below. It may be necessary to perform these procedures at unscheduled time points if deemed clinically necessary by the investigator.

Furthermore, additional evaluations/testing may be deemed necessary by the Sponsor for reasons related to subject safety.

6.2 DETAILS OF TRIAL PROCEDURES AT SELECTED VISITS**6.2.1 Screening and run-in period(s)**

Baseline medical history and demographics, prior and concomitant medications, physical exam, weight, height, vital signs, ECOG performance status, laboratory assessments (CBC with differential, CMP, Magnesium levels, pregnancy test for women of reproductive age and coagulation studies if on anticoagulant therapy), EKG, CT or MRI of involved disease sites, HPV status (determined by p16 IHC staining) and a tumor biopsy (where feasible, obtained after progression on previous line of treatment), will be obtained for all patients at the initial screening visit after they sign the consent form.

Medical history and demographics, prior and concomitant medications, physical exam, weight, height, vital signs, ECOG performance status, and laboratory assessments should be obtained within 48 hours of initiation of treatment, EKG and imaging should be obtained within 28 days of treatment initiation.

6.2.2 Treatment period(s)

During the treatment period, patients will take afatinib once daily at a dose of 30mg. Subjects will visit clinic on day 1 (+/- 3 days) of each 28 day cycle and prior to every cetuximab dose thereafter. Pre-medication with decadron 10mg, H1 and H2 blockade may precede the initial dose of Cetuximab in week 1 of cycle 1, per the discretion of the treating physician.

Premedication with H1 blockade may be used beyond the initial dose for patients who do not experience an infusion reaction with the loading dose. 30-60 minutes after the recommended pre-medications, cetuximab will be administered intravenously at a dose of 400mg/m² in the first week of treatment (loading dose) and at a dose of 250mg/m² every week thereafter.

Alternatively, cetuximab can also be administered at a dose of 500 mg/m² every 2 weeks.

While on study treatment, patients will be seen prior to every cetuximab dose. During these visits, the following evaluations will be done: adverse event assessment, concomitant medications, physical exam, weight, vital signs and ECOG performance status. Laboratory assessments (CBC with differential, CMP, Magnesium) will also be performed prior to the cetuximab dose, throughout the treatment period. Pregnancy test for reproductive age women and coagulation studies if on anticoagulant therapy will be performed every 4 weeks throughout the treatment period.

For patients who are on afatinib alone due to cetuximab being discontinued for a serious infusion reaction or for any other reason, they will be scheduled for follow-up on days 1 and 15 (+/- 3 days) of the first two 28-day cycles. The following assessments will be performed during these visits: adverse event assessment, concomitant medications, physical exam, weight, vital signs and ECOG performance status, laboratory assessments (CBC with differential, CMP, Magnesium). Pregnancy test for reproductive age women and coagulation studies if on

anticoagulant therapy will be performed every 4 weeks throughout the treatment period. After the first 2 cycles, visits can be scheduled on day 1 of every 28-day cycle (+/- 3 days) per physician discretion.

Tissue biopsies will be repeated, where medically feasible, at the end of cycle 1, and at disease progression or end of treatment if discontinued for reasons other than disease progression.

CT or MRI (at physician discretion) will be performed at the end of cycle 2 (+/- 3 days) and every 2 cycles thereafter (+/- 3 days). Treatment will be discontinued in the event of intolerable side effects or unequivocally progressive disease on clinical exam or surveillance scans.

6.2.3 Follow-up period and Trial Completion

6.2.3.1 End of treatment visit (EOT)

The EOT visit will be performed at the time of permanent discontinuation of trial medication for any reason (within 7 days of treatment discontinuation as defined as the removal of the subject from the study treatment period).

At this visit, patients will undergo the following evaluations: adverse event assessment, concomitant medications, physical exam, weight, vital signs, ECOG performance status, laboratory assessments (CBC with differential, CMP, Magnesium). Tumor assessment and imaging will be performed if applicable.

Tissue biopsies will be repeated at this visit, where medically feasible.

6.2.3.2 Residual effect period (REP)

The REP is defined in Section 5.3.7. The End of REP (EoR) visit should be performed at 30 days (+ 14 days) after permanent discontinuation of the trial medication.

The information collected at this visit should include all new AEs that occurred after EOT and a follow-up of adverse events ongoing at EOT.

Additionally, patients will undergo the following evaluations at this visit: concomitant medications, physical exam, weight, vitals, ECOG performance status, laboratory assessments (CBC with differential, CMP, Magnesium). Tumor assessment and imaging will be performed if applicable.

6.2.3.3 Extended follow-up period

6.2.3.3.1 Follow-up for progression

Additional follow-up visits after the EoR visit will be performed for patients who did not progress on treatment. Visits should occur every 4 weeks (+7 days) for up to 24 weeks.

The follow-up for progression period will end at the earliest if one of the following events is met:

- Completion of the predefined follow-up for progression period
- Lost to follow-up
- Disease progression (either clinical or per RECIST)
- Start of a new anti-cancer therapy
- Death
- End of whole trial as specified in Section 8.6

At the end of the follow-up period, the EoFU (End of Follow-Up) visit will be performed. The EoFU visit will be performed within 14 days of known progression, start of new anti-cancer therapy, or completion of predefined follow-up progression period.

The following will be obtained and / or performed during the follow-up visits and the EoFU visit: adverse event assessment and follow-up of adverse events ongoing since EoR to EoFU, concomitant medications, physical exam, weight, vitals, and ECOG performance status,. Tumor assessment and imaging will be performed if applicable.

Treatment with any other anti-cancer drug including the name and type of the anti-cancer drug and/or best supportive care and the date initiated should be recorded, if applicable. Additionally, the patient's outcome should be recorded, including the date of and reason for death [if applicable], or the date of progressive disease.

6.2.3.3.2 Follow-up for Overall Survival

Patients who discontinued study treatment due to disease progression will have at least a monthly telephone call (+/- 1 week) to ascertain survival status. This will continue until patient death.

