a: Screening history, concomitant medications, physical exam, height, weight, vitals, performance status and laboratory evaluations (including pregnancy test) should be obtained within 2 weeks prior to treatment initiation. Screening EKG and CT scans or MRI should be obtained within 28 days prior to treatment initiation.

b: Tumor sample for correlative analyses can be archival or fresh, should be since the last systemic treatment administered and should be obtained where feasible.

Repeat tumor biopsy to be obtained at end of cycle 1 (4 weeks after treatment initiation, with a window of +1 week), where medically feasible

c: Coagulation studies recommended every 4 weeks (+/- 3 days) only for patients on anticoagulation therapy (excluding a daily baby aspirin).

d: Restaging scans for tumor assessment as appropriate for site of disease to be obtained at end of cycle 2 (8 weeks +/- 3 days), and then every 8 weeks thereafter (+/- 3 days) through the EOR visit, or EoFU visit for patients who discontinued treatment for reasons other than disease progression

e: Repeat tumor biopsy for correlative analyses to be obtained where medically feasible at disease progression or EOT.

f: EOT visit within 7 days of discontinuation from study treatment period.

g: EOR visit at 30 days (window of + 2 weeks) after discontinuation from study treatment period.

h: Additional f/u visits for disease progression to continue every 4 weeks (with a window of +7 days) for a maximum of 24 weeks for patients who discontinued study treatment for reasons other than disease progression.

i: Last visit for disease progression assessment. Follow-up period will continue until progression, start of new anti-cancer therapy, or a max of 24 weeks, whichever comes first. The EoFU visit will be performed within 2 weeks of known progression, start of new anti-cancer therapy, or completion of predefined follow-up progression period.

j: Monthly (+/- 1 week) telephone f/u for survival (to continue until death).

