Treatment will be discontinued in the event of \geq grade 3 drug related toxicities that fail to resolve to Grade 2 despite appropriate supportive care or unequivocally progressive disease on clinical exam or surveillance scans. Treatment may also be discontinued for reasons noted in Section 3.3.4, including clinically significant deterioration of the patient's condition, patient noncompliance, investigator determination that it is no longer in the patient's best interest to continue, pregnancy, or withdrawal of consent. Tissue biopsies will be repeated, where

medically feasible, at the end of cycle 1, and at disease progression or end of treatment if discontinued for reasons other than disease progression.

In the situation where patients withdraw consent for treatment on study, we will permit progression and survival data collection unless they specifically withdraw consent for data collection for the trial.

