3.3.4 Removal of patients from therapy or assessments

Patients may discontinue study treatment at any time. Any patient who discontinues treatment will be encouraged to return to the study center to undergo treatment discontinuation assessments and to receive supportive care as indicated. We will permit progression and survival data collection unless the patient specifically withdraws consent for data collection for

the trial. The primary reason for discontinuation should be recorded. Reasons for discontinuation of a patient by the investigator include, but are not limited to, the following:

- Documented disease progression
- Intolerable side effects, defined as grade 3 or higher drug related toxicity that fails to resolve to Grade 2 despite appropriate supportive care
- Clinically significant deterioration of the patient's condition causing a change in performance status prior to treatment discontinuation
- Patient noncompliance
- Investigator determination that it is not in the patient's best interest to continue participation
- Pregnancy
- Patient withdrawal of consent

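### Section 6.2.3.3.2 names only progression stops for monthly survival calls, while flow chart footnote j sets no such limit; followed as written, 6.2.3.3.2 would censor OS informatively

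*Combined protocol and SAP*

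**What the plan says.** Section 6.2.3.3.2 is the only body section on survival follow-up: "Patients who discontinued study treatment due to disease progression will have at least a monthly telephone call (+/- 1 week) to ascertain survival status". The calls continue until death.

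Flow chart footnote j gives the same schedule with no population attached: "Monthly (+/- 1 week) telephone f/u for survival (to continue until death". Section 6.1 describes how the chart relates to the text: "The Trial Flow Chart summarizes the trial procedures to be performed at each visit".

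Patients who did not progress on treatment follow a different track, in section 6.2.3.3.1. They have an EOR visit at 30 days (+14) after stopping, and then: "Visits should occur every 4 weeks (+7 days) for up to 24 weeks". Footnote i adds: "Follow-up period will continue until progression, start of new anti-cancer therapy, or a max of 24 weeks, whichever comes first". The closing visit is also defined in 6.2.3.3.1: "The EoFU visit will be performed within 14 days of known progression, start of new anti-cancer therapy, or completion of predefined follow-up progression period".

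Sections 3.1 and 3.3.4 allow survival data after discontinuation. Section 3.1 says, of patients who withdraw consent for treatment, that "we will permit progression and survival data collection unless they specifically withdraw consent for data collection for the trial". Section 3.3.4 says the same of any patient who stops: "We will permit progression and survival data collection unless the patient specifically withdraws consent for data collection". Neither schedules a contact.

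Section 6.2.3.4 makes survival follow-up conditional ('if applicable') in its definition of patient completion. Section 7.3 estimates median OS in the cohort by Kaplan-Meier with 1 year of follow-up, and adds Cox models. Neither 7.3 nor 7.4 gives an OS censoring rule.

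**The concern.** Taken alone, 6.2.3.3.2 sorts patients by why they stopped. Those who stopped for progression are called until death. Someone who stops for toxicity and progresses two months later did not discontinue because of progression, so the sentence does not pick that patient up after the EoFU visit. Scheduled contact then ends within about 14 days of progression (or at the EOR visit, if that is later), when the risk of death is rising.

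Kaplan-Meier and Cox both assume that patients censored at a given time have the same future risk as those still followed. Censoring tied to progression breaks that assumption. At stake are the OS median, the 12-month OS estimate and the Cox associations. Section 3.2 says results will be compared with historical controls, so no concurrent arm would share a distortion.

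**Working it through.** The plan states no figure on this point, so there is none to reproduce. The check has two parts.

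**1. Length of scheduled contact after a stop for another reason (sections 6.2.3.2 and 6.2.3.3.1)**

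- No windows: 30 + 24 × 7 = 198 days = 28.3 weeks.
- With the +14-day EOR window and an EoFU visit 14 days after the limit: 44 + 168 + 14 = 226 days = 32.3 weeks.
- Also adding the +7-day visit window: 233 days = 33.3 weeks. Footnote h caps this period at 24 weeks, so this is the most generous reading.
- Even without progression, a patient who stops before day 365 - 198 = 167 loses scheduled contact before one year (day 365 - 233 = 132 on the most generous reading).
- With progression, contact ends at max(stop + 30 d, min(progression + 14 d, stop + 198 d)).

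**2. Effect on Kaplan-Meier OS (simulation, at least 400,000 draws per setting)**

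The documents give no PFS, OS or discontinuation figures for this combination, so every driving input is borrowed or assumed:

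- PFS exponential, median 2.6 months (afatinib alone) or 5.8 months (chemotherapy with cetuximab and erlotinib), both from section 1.1. Progression rate = ln 2 / median = 0.267 or 0.120 per month.
- Median OS 8.1 or 10.6 months (the same erlotinib regimen, ITT and per-protocol, section 1.1). The post-progression death rate is solved to give this median.
- Death without progression at 0 or 0.2 times the post-progression rate (assumed).
- Share f stopping for other reasons: 30%, range 15 to 45% (assumed). Stop rate = f/(1 - f) × (progression rate + pre-progression death rate). For f = 0.30, PFS median 2.6 and no pre-progression death, this is 0.429 × 0.267 = 0.114 per month.
- Patients who stop for progression are followed to death. The others are censored at the contact end above, with 198 or 233 days as the limit.

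Shift = Kaplan-Meier estimate minus truth, with stopping unrelated to prognosis:

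| Share stopping for other reasons | Median OS (months) | 12-month OS (points) |
|---|---|---|
| 15% | +0.1 to +0.2 | +0.3 to +1.7 |
| 30% | +0.2 to +0.6 | +0.8 to +4.1 |
| 45% | +0.4 to +1.2 | +1.3 to +7.5 |

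In the next runs (30% share, 198 days) the patients who stop for other reasons differ in prognosis. The hazard change applies to death, or to death and progression.

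- Half the hazard: median shift -1.0 to +0.3 months; 12-month OS shift -4.9 to +1.6 points.
- Double the hazard: median shift about +0.4 to +1.4 months.

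**Comparison with sampling error.** With exponential survival and no censoring, the SD of the median at n = 50 is (median / ln 2)/√50. This gives 8.1/0.693/7.07 = 1.65 months, or 2.16 months at a median of 10.6. Under the illness-death model at a median of 8.1 it is 1.10 to 1.35 months.

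The model leaves out new anti-cancer therapy, which would end contact sooner. It also leaves out deaths learned of by other routes, which would shrink the shift.

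**The case against.** The strongest reply is that the rest of the protocol points to calls for everyone. Footnote j has no limit by reason. The flow chart places its survival column after the End of Follow-Up column. Section 5.3.7.1 speaks of a survival follow-up period after the EOR or end-of-follow-up visit, and the latter exists only for patients who did not progress on treatment. Section 7.3 estimates OS for the whole cohort. On this view 6.2.3.3.2 is one loosely worded sentence.

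Much of that stands. A reader might infer that the protocol excludes other patients from survival follow-up. The documents do not support that: 6.2.3.3.2 never says so, and calling the chart a summary does not give the body text precedence. No text says which prevails, however, and 6.2.3.4 treats survival follow-up as conditional, so a site can in good faith follow the narrower sentence.

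A reader might also infer that OS would certainly be inflated. That holds only if stopping is unrelated to prognosis, or if those who stop for other reasons do worse. Section 3.3.4 lists toxicity, deterioration, noncompliance, investigator decision, pregnancy and withdrawal together, so the net prognosis of this group is unknown. With half the hazard, most settings give a downward shift.

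Finally, a reader might take section 8.6, which ends the trial at the last EOR or progression follow-up visit, as closing survival calls. Footnote j, 6.2.3.3.2 and 5.3.7.1 fit better with 8.6 ending visits only.

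**Conclusion.** The inconsistency is real and should be reconciled. Section 6.2.3.3.2 and footnote j give different populations for the same calls. Permission to collect survival data in 3.1 and 3.3.4 does not fill the gap, because it schedules nothing. If sites follow footnote j, the problem does not arise. If they follow 6.2.3.3.2, OS censoring depends in practice on the reason for stopping and is often triggered by progression.

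The size is modest: about 0.2 to 0.6 months too high in median OS at a 30% share with stopping unrelated to prognosis, and from about -1.0 to +1.4 months if prognosis differs by a factor of two in hazard. These figures rest on an assumed share and on medians from other regimens, and they assume that no deaths are learned of outside scheduled contact. The shift is generally within sampling error at 50 patients, its sign is not certain, and OS is a secondary endpoint with no stated hypothesis test. ORR and its test are untouched.

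**What to change.** - In 6.2.3.3.2, give the monthly calls to all patients who discontinue study treatment for any reason, unless they withdraw consent for data collection. Start them after the EOR visit or, where there is one, after the EoFU visit.
- State the same population in footnote j.
- In 6.2.3.4, remove the 'if applicable' condition so that survival follow-up covers every patient. Active AE collection need not lengthen, because 5.3.7.1 already ties it to the EOR or end-of-follow-up visit.

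The cost is a wording amendment and telephone calls, with no extra visits or procedures. Up to month 12, a patient who stops very early needs at most about (365 - 198)/30.4 = 5.5, so 6 calls, if the full contact period was used, and (365 - 30)/30.4 = 11 if contact ended at EOR. Calls until death would add more for longer survivors. Survival status of patients already off treatment may still be recoverable, since 3.1 and 3.3.4 permit its collection.

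Optional clarifications, separate from this point: say in 8.6 that survival calls may outlast the final visits, set an OS data cut, and define in 7.3 what 1 year of follow-up means.
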